#### 7.2.2 The level of statistical significance

The statistical significance level will be 5%

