- Not more (or minimum) condensation of the lens surface of the disposable lens as compared to the reusable lens since each disposable lens will have an intact coating.

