## 2 Objectives and Design

### 2.1 Study objectives and hypotheses

This study is designed to obtain more information on the efficacy of the disposable RESIGHT lenses in routine vitrectomy surgery. This information can lead to adjustments to these surgical lenses to further fine tune a device which can be used by other surgeons.

[figure not shown]
Theoretically, both the improved lens design and better resistance to fogging should improve the visualization of the retina hence facilitate the surgery, increasing the surgical safety.

During the surgery, a comparison will be done between the present lenses used (reusable RESIGHT lenses and disposable Vitreq contact lens) and the new disposable RESIGHT lenses. For that purpose, both lenses will be mounted on the rotating arm of the RESIGHT allowing the surgeon to toggle between both lenses during surgery. This toggling takes a few seconds, hence the total surgery time may be extended by ~30 seconds. However, this will most likely not impact patient safety since a vitrectomy surgery typically requires one hour time.

To compare the image generated by the present and the new RESIGHT lenses, both still shots and (short) video recordings will be created during the surgery. For this purpose, the internal camera and recording system of the ARTEVO microscope will be used. This will not have any impact on the surgery duration. Since only the retinal image is recorded, there is no risk of patient recognition on the recorded photos and videos.

Moreover, the Artevo microscope has a function that generates anonymous data export which will protect the patients' identity.

Although there is no contact between the lens and the patient, the lens is touched by the surgeons' glove, hence must be sterile. ZEISS will deliver these lenses pre-sterilized according to the present required standards. ZEISS will provide these lenses packaged and labeled according to their specifications.

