## 2.2 Primary Endpoints

The purpose of this study is to evaluate the intra-operative efficacy of new intra-operative viewing device, more specifically:

[figure not shown]
1. To determine whether the performance of the disposable MACULA LENS is comparable or even better than a flat contact lens, due to its improved resolution. For this purpose, the in-house available Vitreq contact lens will be used.  
This parameter will be determined in the macular surgery study arm only.
2. To determine that the disposable ULTRA WIDE-ANGLE LENS does not condensate / condensates to a lesser extent during surgery.  
This parameter will be determined in both study arms.
3. To determine that the disposable ULTRA WIDE-ANGLE LENS allows for imaging up to ora serrata on human eyes, reducing the need for indenting. This parameter will be determined in the retinal detachment surgery study arm only.
4. To evaluate whether both peripheral vitrectomy as well as macula work are possible with the disposable wide-angle lens. This parameter will be determined in the macular surgery study arm only.
5. To evaluate the amount of fogging that occurs when using the disposable wide-angle lens compared to using the reusable yellow lens.
6. To evaluate whether the amount of light to illuminate the retina is reduced when using any of the disposable lenses compared to the reusable yellow/green lenses. This parameter will be

determined in both study arms.

7. To evaluate whether the disposable lenses show a more natural color representation compared to the reusable yellow and green lenses. This parameter will be determined in both study arms.
8. To evaluate whether the iOCT quality recorded with the disposable macula lens is similar to or better than the iOCT recorded using the green reusable lens. This parameter will be determined in the macular surgery study arm only, where iOCT is being recorded as standard-of-care.

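### Eight unranked primary endpoints share one 5% level, with no stated order, multiplicity adjustment or success rule

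*Combined protocol and SAP*

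**What the plan says.** Section 2.2 numbers eight items as primary endpoints, and nothing says that the numbers set a testing order. The synopsis enters a slash for secondary objectives, so there is no lower tier. Section 7.2.1 applies the same choice of tests to every endpoint. Section 7.2.2 is one sentence: "The statistical significance level will be 5" per cent. It does not say whether this is per test or overall, or whether it is one- or two-sided.

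The eight items differ in kind:

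- **Items 5, 6 and 7** (fogging, light, colour) are comparisons with the reusable lenses. Item 5 names no cohort. Item 6 asks "whether the amount of light to illuminate the retina is reduced when using any of the disposable lenses", which leaves the lens contrast open.
- **Items 1 and 8** name a comparator but mix equivalence with superiority, and give no margin: "the performance of the disposable MACULA LENS is comparable or even better than a flat contact lens" and "similar to or better than the iOCT recorded using the green reusable lens".
- **Items 2 and 3** (ultra-wide lens: condensation, and view to the ora serrata) name no comparator in section 2.2. For condensation, section 1.2 points to the reusable lens in general terms ("condensation of the lens surface of the disposable lens as compared to the reusable lens").
- **Item 4** is a feasibility question: "To evaluate whether both peripheral vitrectomy as well as macula work are possible with the disposable wide-angle lens".

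Section 7.2.3 plans a sensitivity analysis on a primary outcome in the singular, while section 2.3 uses the plural. Section 7 refers to a study-specific SAP for detail. Section 7.2.4 requires the final statistical plan to be agreed before data lock and before any analysis.

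**The concern.** When several endpoints are all primary and each is tested at 5%, the 5% holds for each test but not for the set, unless the plan says how the results combine. Nothing in the text prevents any single primary result with p<0.05 from being reported as a positive primary finding, and section 10.2 states that publication is intended.

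The number of formal tests is also undefined, so a statistician could not build an adjustment from the protocol as it stands. Separately, the sensitivity analysis in section 7.2.3 cannot be run as written, because its target could be any of eight outcomes. That second problem does not depend on any assumption about error rates.

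**Working it through.** **The plan's own figure.** The 5% is a setting, not a result, so there is nothing to reproduce. Section 7.1 gives only 120 eyes in two cohorts, with no effect size, variance, margin or power.

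**Inputs from the documents.** Level 5% (section 7.2.2); eight primary items (section 2.2); 60 eyes per cohort (synopsis and section 2.3); no interim analysis (section 7.3).

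**Assumptions.** All null hypotheses are true; tests are two-sided at 5%; there is one test per item; any one significant result may be claimed; test statistics share a common correlation r of 0, 0.5 or 0.9. Item 4 is treated as descriptive, so the largest family is seven.

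**Independent tests.** Family-wise rate = 1 − 0.95^k:

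- k = 3: 1 − 0.95^3 = 0.1426
- k = 5: 1 − 0.95^5 = 0.2262
- k = 7: 1 − 0.95^7 = 0.3017

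**Correlated tests.** With c = 1.96 and x standard normal, family-wise rate = 1 − E{[Φ((c − √r·x)/√(1−r)) − Φ((−c − √r·x)/√(1−r))]^k}, by numerical integration.

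| Tests (items) | r = 0 | r = 0.5 | r = 0.9 |
|---|---|---|---|
| 3 (5, 6, 7) | 14.3% | 12.5% | 8.4% |
| 5 (adding 1, 8) | 22.6% | 18.3% | 10.2% |
| 7 (adding 2, 3) | 30.2% | 23.0% | 11.4% |

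The single-test rate for comparison is 5%. Counting only results that favour the new lens (single-test rate 2.5%), three tests give 7.3%, 6.3% and 4.2%, and five give 11.9%, 9.1% and 5.1%.

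**Effect of the undefined family.** Section 2.2 assigns items 6 and 7 to both arms and leaves item 5 unassigned. If these three were each tested per arm (assumed), there would be six tests: 1 − 0.95^6 = 26.5% under independence, against 14.3% for three. Testing items 6 and 7 lens by lens would raise it further.

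**Power cost of Holm.** No outcome scale or power target is stated in the text available. Assume a continuous paired outcome in 60 eyes (t test, 59 degrees of freedom). The standardised difference with 80% power at 5% is 0.368, so the noncentrality is 0.368 × √60 = 2.85. At Holm's strictest step the level is 0.05/k:

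- k = 3: level 0.0167, power 65%
- k = 5: level 0.0100, power 58%
- k = 7: level 0.0071, power 53%

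**The case against.** The strongest reply is that the inflation rests on a success rule the plan never states. Section 2.1 gives the aim modestly ("This study is designed to obtain more information on the efficacy of the disposable RESIGHT lenses in routine vitrectomy surgery"), and the design is a non-randomised case study. If all primary items had to succeed, testing each at 5% would not inflate the error. This stands, and it makes every percentage above conditional. It does not remove the gap, because the plan labels the items primary, sets a significance level, and states neither rule.

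The study-specific SAP may already contain a rule. That also stands; if it does, it needs only to be stated in section 7.2.2.

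The synopsis and section 2.1 name the reusable lenses and the contact lens as comparators for the study as a whole, so items 2 and 3 are not without context. But neither place says which comparator belongs to which item.

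Two stronger readings are tempting. One takes all eight items as tests and quotes 33.7% under independence. Item 4 asks only whether work is possible, so the documents do not support eight comparative tests. The other is that the lead endpoint could be picked after results are known, since the surgeon switches lenses ("allowing the surgeon to toggle between both lenses during surgery") and records the outcomes. The documents limit that inference: section 7.2.4 requires agreement before any analysis, section 9.4 bars planned deviations, and section 9.7 requires authorisation of substantial amendments. These controls set no hierarchy, but they do not leave endpoint choice freely open.

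**Conclusion.** The gap is real and should be closed. The text defines neither the set of formal primary tests nor how their results combine at the 5% level, and section 7.2.3 has no identifiable target.

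The size is conditional. If any one primary result may be claimed, the two-sided family-wise rate runs from 8.4% (three tests, correlation 0.9) to 30.2% (seven independent tests). These are scenario values, not bounds: the correlations and one test per item are assumed. Endpoints measured on the same eyes are likely to be correlated, which favours the lower figures; splitting by arm or lens would push them up.

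A reader should not infer that the plan declares success on one positive endpoint, because no section says so. Confidence is moderate, because the separate SAP cannot be seen beyond section 7.

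**What to change.** In section 7.2.2, do one of the following.

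- **(a)** Name one primary endpoint with its cohort and lens contrast, and make the others secondary.
- **(b)** Apply Holm at a family-wise 5% to a fixed, listed set of primary tests. Give each test one lens contrast, one comparator and one population (pooled or a named arm). This applies to items 2, 5, 6 and 7 wherever they are used, and item 3 needs a comparator before it can join. Report the remaining items descriptively with confidence intervals: item 4, and items 1 and 8 unless they are tested for superiority, since no margin is given.

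Under either option, point the section 7.2.3 sensitivity analysis at the named endpoint or endpoints. Record the choice before the first eye is enrolled, or as an approved amendment before any outcome data are reviewed. If the SAP already holds a rule, state it in section 7.2.2.

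**Cost.** No extra eyes or procedures. Option (b) lowers per-endpoint power at the strictest step from 80% to about 65%, 58% or 53% for three, five or seven tests, under the assumptions shown. Option (a) loses no power on the named endpoint, but the others can no longer be primary claims. Either change may need ethics committee and competent authority approval as a substantial amendment under section 9.7.

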#### 7.2.3 Procedure for accounting for missing, unused and spurious data

Missing data

In case of missing values, the underlying missingness process (MCAR, MAR or MNAR) will be investigated and 5 multiple imputations will be performed using the **MICE** R package.

We will test with the statistical test of Jamshidian and Jalal (2010), implemented in the MissMech R Package (Jamshidian, Jalal & Jansen, 2014), whether missing data were MCAR. If they were not MCAR, we investigated whether or not the missing mechanism could be explained by baseline characteristics (eg, sociodemographic, medical features) of patients using logistic regression, which would suggest an MAR mechanism. If missing data were not MCAR or MAR, they were considered as MNAR.

A sensitivity analysis will be performed on the primary outcome on the aggregated datasets from the multiple imputation.

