## STUDY FLOWCHART

### Schedule of Events – Study specific Procedures / Assessments

[figure not shown]
**i** Please indicate in the flowchart with different colors whether a procedure is performed as part of the **standard of care** or **specifically for the Investigation**. Describe the visits and applicable procedures/investigations (with a reference number or letter) in more detail in a footnote below the study flowchart

Procedures/ Assessment	Pre-surgery	Surgery
Timing (weeks)	0	0
Informed consent	X 	
Inclusion / Exclusion criteria	X	
Randomisation	X	
Vitrectomy +/- Phaco parameters		X
Device Deficiencies		X
(Serious) Adverse event (S)(AE) assessment		X

*1 : Informed Consent process should take place prior to all other study-related procedures at the screening visit*

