### 2.3 Design of the Clinical Investigation

Investigator-initiated, academic, mono-center, prospective, interventional case study. No randomization will be performed.

Sixty eyes will be enrolled in two study arms:

- Group 1: 60 eyes that undergo primary vitrectomy surgery for retinal detachment
- Group 2: 60 eyes that undergo macular surgery: pucker, vitreomacular traction or macular hole.

The study duration for the participants starts from the moment the patient is informed.

After the surgical procedure, the surgeon will record the parameters that are required to determine the primary outcomes of the study (§6). These parameters will be recorded in a Formasa form specifically designed for this study: see attached document. No information will be collected in this document that can identify the patients, the only clinical information used is the indication of the surgery (since this impacts the primary outcome parameters collected). After all patients (120 eyes) will be included in the trial, a KWS query will be used to export the Formasa forms. Only the content of these forms will be exported for statistical analysis.

In case a device deficiency occurs (any issue that hinders the surgery when using a disposable RESIGHT lens), it will be recorded in the Device Deficiency form (see attachment). Additionally, any (Serious) Adverse Event resulting from such Device Deficiency will be recorded in the (S)AE form (see attachment).

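### Section 7.2.3 labels missing data MNAR by elimination, attaches no consequence to the label, and specifies no analysis that departs from MAR

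*Combined protocol and SAP*

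**What the plan says.** Section 7.2.3 of the combined protocol and SAP gives one rule for any missing value: "the underlying missingness process (MCAR, MAR or MNAR) will be investigated and 5 multiple imputations will be performed using the" MICE R package. It then sets out a three-step classification.

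- A named test, run in the MissMech package, decides whether the data are MCAR.
- If they are not, the next question is whether missingness "could be explained by baseline characteristics (eg, sociodemographic, medical features) of patients using logistic regression". A positive answer is taken to suggest MAR.
- What remains is settled by elimination: "If missing data were not MCAR or MAR, they were considered as MNAR".

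The section ends with its only sensitivity analysis: "A sensitivity analysis will be performed on the primary outcome on the aggregated datasets from the multiple imputation".

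Three other places bear on this. Section 7.2.5 keeps every eye in the analysis. Section 7 refers to a study-specific SAP for detail. Section 7.2.4 lets the final statistical plan be agreed before data lock. None of them adds a missing-data rule.

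**The concern.** The plan names MNAR as a possible finding and then does nothing with it. An analyst who reaches that label still runs the same imputation. No MNAR model is given, and a package name does not supply one; chained equations in their standard use assume MAR.

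The label is also not something that the data can show. MAR and MNAR differ in whether missingness depends on the unseen value, and the unseen value is by definition not available to a regression.

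At stake is the reading of a comparison in which some disposable-lens ratings are blank. If a blank is related to how the lens performed, imputation under MAR fills it from eyes where the lens was rated. A sensitivity analysis on those same datasets cannot show how far the conclusion depends on that step.

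**Working it through.** The plan has no figure to reproduce: it gives no missing-data rate, effect size or standard deviation. The check is therefore textual, followed by an illustration on assumed inputs.

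**1. What each label leads to under Section 7.2.3**

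| Label | How it is reached | Imputation | Sensitivity analysis |
|---|---|---|---|
| MCAR | test does not reject | 5 in MICE | on the imputed datasets |
| MAR | test rejects, baseline regression explains missingness | 5 in MICE | on the imputed datasets |
| MNAR | test rejects, baseline regression does not explain missingness | 5 in MICE | on the imputed datasets |

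The last two columns do not vary. Sections 7 to 7.3 contain no delta shift, tipping-point, pattern-mixture, selection-model or worst/best-case analysis.

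**2. Whether the label can be established.** Suppose the baseline regression finds nothing. That fits at least three situations: too few blanks for the regression to detect anything; missingness that depends on other observed ratings of the same eye, which is still MAR although no baseline variable shows it; and true MNAR. Suppose instead that it finds an association. Missingness may still depend on the unseen rating as well. Neither result separates MAR from MNAR.

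**3. Whether the sensitivity analysis could be a departure from MAR.** One reading is that the main analysis uses complete cases and the imputed analysis is the contrast. The complete-case side takes rated eyes to stand for blank ones. The imputed side does so after conditioning on observed data. Neither lets a blank depend on its own unseen value.

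**4. Illustrative size, categorical rating.** Inputs: n = 60 eyes per cohort (CIP Synopsis and Section 2.3); a binary endpoint and k blank eyes are assumed.

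Width of worst-to-best bounds = k/60:

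- k = 0: 0 points
- k = 1: 1/60 = 1.7 points
- k = 3: 3/60 = 5.0 points
- k = 6: 6/60 = 10 points
- k = 12: 12/60 = 20 points

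For scale, the 95% half-width for a proportion is 1.96 × √(p(1 − p)/60). That is 12.7 points at p = 0.50, 11.6 at p = 0.70 and 5.5 at p = 0.95.

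Example with k = 3 and 54 of the 57 rated eyes favourable: the rated proportion is 54/57 = 94.7%, the worst case 54/60 = 90.0%, the best case 57/60 = 95.0%. Imputation under MAR with uninformative predictors would centre near 94.7%, which is 4.7 points above the worst case. Informative predictors would reduce that gap.

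**5. Illustrative size, continuous rating.** Assume a within-eye difference whose missing values are shifted by δ = 0.5 SD. The mean moves by (missing fraction) × δ, and one standard error is 1/√60 = 0.129 SD.

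- 5% missing: 0.025 SD, or 0.19 SE
- 10% missing: 0.05 SD, or 0.39 SE
- 20% missing: 0.10 SD, or 0.77 SE

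A result at z = 2.5 under MAR would fall to 1.96 when δ = (2.5 − 1.96)/(√60 × fraction): 1.39, 0.70 and 0.35 SD respectively. The omission matters little at 5% missing and can matter at 20%.

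**The case against.** The strongest reply is that little will be missing. Each eye has one operation and no study visits, and the surgeon fills in the form afterwards: "After the surgical procedure, the surgeon will record the parameters that are required to determine the primary outcomes of the study". Section 8.1.1.1 makes the investigator answerable for complete forms, and Section 8.1.1.3 provides for queries. Fogging and poor view are themselves what the endpoints measure, so a weak lens should produce a poor rating, not an empty field. This stands, and it is why the point is minor. It does not rescue a classification rule that is invalid whenever it is used.

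A second reply is that the study-specific SAP or the final plan may contain an MNAR analysis. That is possible, so the finding is limited to what the supplied text specifies.

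Several stronger inferences are tempting, but the documents do not support them.

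- *Lens replacement will create informative blanks.* Section 2.4 and the Device Deficiency definition foresee a faulty lens being replaced. The latter expects the fault to be seen at the start of surgery and allows another disposable sample, so the eye may still be rated. The form is not reproduced and may have a category for this.
- *The regression lacks its inputs.* Section 2.3 says "the only clinical information used is the indication of the surgery", but in the context of not identifying patients. The schedule of events lists "Vitrectomy +/- Phaco parameters", and Section 4.2 refers to data from the standard clinical path. What is collected cannot be settled without the form.
- *Device Deficiency records will not reach the statistician.* Section 2.3 says of the surgeon's forms: "Only the content of these forms will be exported for statistical analysis". Yet Section 7 describes an export from the eCRF, and Section 8 places the Device Deficiency form in that eCRF. The inference holds only if Section 2.3 is preferred.
- *Every eye with a deficiency record should count as a failure.* Deficiencies include use errors and inadequate manufacturer information, so a record does not by itself mean a poor view.

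**Conclusion.** The point holds as a minor one. Section 7.2.3 assigns MNAR by elimination on evidence that cannot establish it, attaches no consequence to the label, runs the same imputation in every case, and specifies no analysis that departs from MAR.

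The effect is nil with no blank ratings and small with few. The 1.7 points per blank eye rests on an assumed binary endpoint in a cohort of 60, and the shifts for continuous ratings rest on assumed missing fractions and an assumed δ. A reader might infer that the results will be biased towards the disposable lenses. The documents do not support that: they give no missing-data rate and no evidence that blanks would follow poor lens performance.

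**What to change.** Change Section 7.2.3 before data lock, which Section 7.2.4 allows.

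- **Keep** the five imputations and the planned analysis on the imputed datasets.
- **Drop** the MCAR/MAR/MNAR classification as a conclusion. Report the MCAR test and the logistic regression as descriptive only.
- **Add**, for any endpoint with missing disposable-lens ratings, a pre-specified sensitivity analysis that departs from MAR: worst-case and best-case bounds for categorical ratings, and a delta shift or worst rank for continuous ones. State the scale and the unfavourable direction for each endpoint. Keep every actual rating unchanged.
- **Limit** any targeted worst case to an unrated eye whose Device Deficiency record shows that the lens itself impaired the view relevant to that endpoint.

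The cost is a few sentences, slightly more analysis and wider reported uncertainty. If no rating is blank, the added analysis is not needed and nothing changes.

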### 7.1 Sample Size Determination

120 eyes in 2 cohorts

.

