### 7.2.5 Inclusion in analysis

All eyes will be included in the analysis.

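### Five imputations with no stated seed: if more than a few per cent of values are missing, a sensitivity p-value near 0.05 can cross the 5% line by seed alone

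*Combined protocol and SAP*

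**What the plan says.** Section 7.2.3 of the combined protocol and SAP deals with missing values: "5 multiple imputations will be performed using the" MICE R package. The same section gives the imputed data their role: "A sensitivity analysis will be performed on the primary outcome on the aggregated datasets from the multiple imputation". It states no expected missing rate, imputation model, pooling rule or seed, and no reason for choosing five.

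Section 7.2.2 sets the decision line: "The statistical significance level will be 5" per cent, without saying whether tests are one- or two-sided. Section 7.1 gives only "120 eyes in 2 cohorts", and section 2.3 splits these equally ("Group 1: 60 eyes that undergo primary vitrectomy surgery for retinal detachment", and the same number for macular surgery). Section 7.2.5 adds: "All eyes will be included in the analysis". Section 7.2.4 leaves the final statistical plan to be agreed before data lock.

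**The concern.** Multiple imputation draws random values, so its pooled result carries Monte Carlo error that shrinks as the number of imputations, m, grows. With m = 5 that error can be large enough to move a borderline p-value across 5%. This happens even when the five datasets are pooled correctly.

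The imputed analysis is the only robustness check on missing data that the plan names. Section 2.2 lists eight primary endpoints, section 7.2.1 covers all of them with the same tests, and section 7.1 shows no power calculation. A p-value near 0.05 somewhere is therefore a realistic prospect. For such an endpoint, the check could agree or disagree with the main analysis because of the seed and not because of the data.

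**Working it through.** There is no figure of the plan's to reproduce: five is stated without derivation. The check asks how far the pooled p-value moves when only the seed changes.

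**Inputs from the documents**
- m = 5 (section 7.2.3); significance level 5% (section 7.2.2), taken as two-sided.
- 60 eyes per cohort (section 2.3). Endpoints 2, 6 and 7 use both cohorts (section 2.2), so up to 120 eyes.
- Paired comparison within an eye: "both lenses will be mounted on the rotating arm of the RESIGHT allowing the surgeon to toggle between both lenses during surgery" (section 2.1).

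**Assumptions**
- Continuous score, correlation 0.5 between lenses.
- One lens's score missing completely at random in 2% to 30% of eyes. In a cohort of 60 that is about 1, 3, 6, 12 or 18 eyes for 2%, 5%, 10%, 20% and 30%.

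**Step 1: formula.** Let W be the mean within-imputation variance and B the between-imputation variance. Rubin's total variance is T = W + (1 + 1/m)B. The seed adds variance B/m to the pooled estimate. In standard-error units its SD is about sqrt(FMI/m), where FMI = B/(W + B) is the fraction of missing information.

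| FMI | m = 5 | m = 50 |
|---|---|---|
| 5% | sqrt(0.05/5) = 0.10 | sqrt(0.05/50) = 0.03 |
| 10% | sqrt(0.10/5) = 0.14 | sqrt(0.10/50) = 0.04 |
| 30% | sqrt(0.30/5) = 0.24 | sqrt(0.30/50) = 0.08 |

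Going from 5 to 50 imputations cuts this noise by sqrt(10), about 3.2-fold. The seed's share of the total variance of z is (FMI/m)/(1 + FMI/m). At m = 5 this is 0.01/1.01 = 1% for FMI 5%, 0.02/1.02 = 2% for 10%, 0.06/1.06 = 6% for 30% and 0.10/1.10 = 9% for 50%. The formula covers the pooled estimate only. The estimate of B also varies with the seed, so step 2 simulates the whole p-value.

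**Step 2: simulation.** Imputation was by Bayesian normal regression, pooled by Rubin's rules with Barnard-Rubin degrees of freedom. Each dataset was shifted so that very many imputations would give p = 0.03. It was then re-imputed 600 times, on 20 datasets per scenario. Results for 60 pairs:

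| Missing | m = 5: middle 95% of p | m = 5: seeds with p ≥ 0.05 | m = 50: middle 95% of p | m = 50: seeds with p ≥ 0.05 |
|---|---|---|---|---|
| 2% | 0.024 to 0.040 | 0.1% | 0.028 to 0.033 | 0% |
| 5% | 0.020 to 0.050 | 3% | 0.026 to 0.035 | 0% |
| 10% | 0.016 to 0.065 | 10% | 0.025 to 0.038 | 0% |
| 20% | 0.011 to 0.100 | 25% | 0.022 to 0.043 | 0.3% |
| 30% | 0.007 to 0.137 | 33% | 0.019 to 0.048 | 1.6% |

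A separate repeat of the simulation gave about 2%, 10%, 23% and 33% at m = 5 for 5% to 30% missing, and at most 1.7% at m = 50.

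**Step 3: clear results.** With m = 5 and a large-m p of 0.005, the conclusion changes in 0% of seeds up to 10% missing, 0.6% at 20% and 2.7% at 30%. With a large-m p of 0.20 it changes in at most 0.3% at every rate.

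**Step 4: sample size.** At 120 pairs, 10% missing, m = 5 and a large-m p of 0.03, the range is 0.016 to 0.063 and 10% of seeds cross. At 60 pairs it is 0.016 to 0.065 and also 10%.

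**The case against.** The strongest answer is that the problem may never arise. Participation covers one operation and adds no study visits. Section 2.3 says "After the surgical procedure, the surgeon will record the parameters that are required to determine the primary outcomes of the study". Section 8.1.1 makes the investigator responsible for complete forms and has a data manager query inconsistencies. A low missing rate is a fair inference, and at 2% missing the effect all but vanishes. This stands: the documents give no rate, so the size can only be conditional.

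Three further objections also stand, in part:
- The plan labels this a sensitivity analysis, and section 7.2.4 leaves time to settle details. That limits the consequence but does not remove the stated five. Nor does the plan say how an eye with a missing value enters the main analysis.
- Several endpoints read as yes/no or graded judgements, and section 7.2.1 also plans rank and chi-squared tests. The percentages above belong to a continuous paired score and do not carry over to those tests.
- More imputations do not settle a result lying on the line. In a single simulated dataset with 30% missing and a large-m p of about 0.04, the share of seeds above 0.05 was 50% at m = 5, 21% at m = 50 and 12% at m = 100.

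A reader might infer that a second analyst could not reproduce the result because m is five. That is not so: a recorded seed makes m = 5 exactly reproducible, and without one m = 50 is not exactly reproducible either. The reproducibility gap is the unstated seed.

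**Conclusion.** The point holds as a minor one. Five imputations are unjustified, and no seed is given. Under the assumptions listed, a sensitivity p-value near 0.05 is exposed to the seed once more than a few per cent of values are missing: from 2 to 3% of seeds at 5% missing up to about 33% at 30%, for a large-m p of 0.03. With 50 imputations the figure is under 2% at every rate examined.

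Two stronger readings are not supported. One is that the sensitivity result is largely a product of the seed. By the step 1 formula the seed contributes about 9% of the variance of z even at an FMI of 50%, and clear results almost never change. The other is that the small sample is the cause. The noise depends on the fraction of missing information and on m, and 60 and 120 pairs behave alike. Nothing here shows that a main-analysis conclusion is at risk.

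**What to change.** In section 7.2.3, replace five by at least 50 imputations, and by 100 if more than 20% of an endpoint's values are missing. Fix the seed in the SAP and record it with the results, so that the analysis can be repeated exactly. State that pooling follows Rubin's rules, and report the Monte Carlo standard error of the pooled estimate, sqrt(B/m), beside it. A result still close to 5% can then be seen for what it is.

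The cost is a few words and negligible computing time: 50 draws for one variable took under a millisecond in Python, though the MICE package itself was not timed. The change fits within the finalisation before data lock that section 7.2.4 foresees.
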